8.3.2. Screening visit 2: Ophthalmological assessment

Details of the ophthalmological assessment are given in Section 8.5.4. Screening

Visit 2 will take place after confirmation that all other eligibility criteria have been met and may take place up to and including Day –3.

Subjects will be scheduled to report to the Investigator site for admission to the ward on Day –3.

8.3.3. Admission to Ward (Day –3)

Subjects will be admitted to the ward at the Phase 1 Unit, on Day –3 at approximately 1600 h, and will have a urinary drug screen and alcohol breath test, and be monitored for AEs.

Subjects will fast overnight from 2300 h until after their assessments are complete on the morning of Day –2 (about 13 h in total).

8.3.4. Day –2

Blood samples will be taken for measurement of glucose and insulin for the OGTT at times as per the Schedule of events in Section 5.

Subjects will be given a high glucose liquid to drink after their first sample (–48 h) is taken. The glucose and insulin measurements taken at 1, 2 and 4 h after the –48 h sample (–47, –46 and –44 h) will be used to complete the OGTT. After those samples are taken, subjects will have their first meal of the day. Subjects will be monitored for AEs.

Subjects will fast overnight for at least 9 h before the –24 h time point on Day –1, until at least the –20 h timepoint on Day –1.

8.3.5. Pre-day (Day –1)

On the morning of Day –1, a cannula will be inserted into a forearm vein, under local anaesthesia with lidocaine 0.5%, for withdrawal of venous blood (for glucose, insulin, glucagon and cortisol measurements).

Subjects will have the following procedures completed as scheduled in Section 5, time-matched to Day 0:

- Scheduled AE monitoring
- Short physical examination and neurological assessments (including body weight, once in the morning)
- 12-lead ECGs (in triplicate only at –24 h)
- Vital signs (including oral temperature)
- Clinical safety laboratory evaluations (haematology, coagulation, biochemistry, urinalysis)
- Blood samples will be taken for measurement of glucose, insulin, glucagon and cortisol

Subjects will fast overnight as described in Section 4.3.

8.3.6. Profile day (Day 0)

Eligibility (based on inclusion and exclusion criteria) must be determined before

subject randomisation.

On the morning of Day 0, a cannula will be inserted into a forearm vein, under local anaesthesia with lidocaine 0.5%, for withdrawal of venous blood. The following will be done within 0.75 h before the morning dose of study medication and at the time points after administration outlined in the Schedule of Events (Section 5):

- Scheduled AE monitoring (particularly any event related to the CNS)
- Neurological examinations – full before the morning dose, and short at all other time points
- Short physical examinations
- 12-lead ECGs (in triplicate only at the pre-dose measurement)
- Vital signs (BP and HR)
- Clinical safety laboratory evaluations (haematology, coagulation, biochemistry, urinalysis)
- Blood sampling to assay glucose, insulin, glucagon and cortisol
- Blood sampling to assay pre-dose emodepside and its metabolites in plasma (with frequent sampling after dosing)

Subjects in Cohort 3 will have an additional evening dose of the study medication, approximately 12 h after their morning dose.

Subjects will fast overnight, each night, as described in Section 4.3.

8.3.7. Repeat dosing period (Days 1–8)

Subjects will have the following assessments at the time points specified in the Schedule of Events (Section 5):

- Scheduled AE monitoring (particularly any event related to the CNS)
- Short neurological examination
- Physical examination – full on Days 3–8 and short on Days 1 and 2
- 12-lead ECGs (single measurements)
- Vital signs (BP and HR)
- Blood sampling for the OGTT (Days 1 and 8 only). Subjects will be given a high glucose liquid to drink after their first sample is taken, as done on Day –2.
- Blood sampling to assay glucose, insulin, glucagon and cortisol (Day 1 only)
- Blood sampling to assay pre-dose emodepside in plasma
- Clinical safety laboratory evaluations (haematology, coagulation, biochemistry, urinalysis), on Days 1, 5, and 8 only

Subjects will fast overnight, as described in Section 4.3.

8.3.8. Profile day (Day 9)

On the morning of Day 9, a cannula will be inserted into a forearm vein, under local anaesthesia with lidocaine 0.5%, for withdrawal of venous blood. The following will be done within 0.5 h before the morning dose of study medication and at the time points after administration outlined in the Schedule of Events (Section 5):

- Scheduled AE monitoring (particularly any event related to the CNS)
- Short neurological and physical examinations
- 12-lead ECGs (in triplicate only at the pre-dose measurement)
- Vital signs (BP and HR)
- Clinical safety laboratory evaluations (haematology, coagulation, biochemistry, urinalysis)
- Blood sampling to assay glucose, insulin, glucagon, cortisol
- Blood sampling to assay leptin and prolactin
- Blood sampling to assay pre-dose emodepside and its metabolites in plasma

Subjects in Cohort 3 will have a final morning dose of the study medication only on Day 9.

Subjects will fast overnight, as described in Section 4.3.

8.3.9. Days 10–14

Subjects will remain on the ward for another 5 days, and have the following assessments at the time points outlined in the Schedule of Events (Section 5):

- Scheduled AE monitoring (particularly any event related to the CNS)
- Physical examination and neurological assessments – short on Days 10-13 and full on Day 14
- Ophthalmological assessments (Day 10 only)
- 12-lead ECGs (single measurements; on Days 10, 12 and 14 only)
- Vital signs (BP and HR)
- Clinical safety laboratory evaluations (haematology, coagulation, biochemistry, urinalysis) (on Days 10 and 14 only)
- Blood sampling to assay glucose, insulin, glucagon and cortisol
- Blood sampling to assay post-dose emodepside in plasma

Subjects will fast during this period as described in Section 4.3.

Subjects may be discharged from the ward following completion of their Day 14 assessments.

8.3.10. Outpatient Visits (Days 17, 20, 23 and 27), Follow-up Visit (Day 30), and long-term follow-up Visits (Days 60, 90 and 120) ± 2 days

Subjects will return to the clinic for each ambulatory visit, and the Follow-up visit, as scheduled in the Schedule of events (Section 5), to have some or all of the following procedures:

- Scheduled AE monitoring (particularly any event related to the CNS)
- Physical examination – short on Days 17, 20, 23, 27, 60, 90 and 120, and full at Day 30
- Short neurological assessments
- Vital signs (BP and HR)
- 12-lead ECGs (single measurements)
- Clinical safety laboratory evaluations (haematology, coagulation, biochemistry, urinalysis) on Days 23, 30, 60, 90 and 120 only (haematology will include HbA1C on Day 120 only)
- Blood sampling to assay post-dose emodepside in plasma
- Alcohol breath tests on Days 60, 90 and 120 only
- Blood sampling for the OGTT (Day 120 only). Subjects will be given a high glucose liquid to drink after their first sample is taken, as done on Days –2, 1 and 8.

Subjects will fast overnight before their Day 23 and Day 30 visit, and all long-term follow-up visits, as described in Section 4.3.

If deemed necessary by the ophthalmologist additional ophthalmology follow-up visit(s) may be scheduled to characterize and assess any eye-related AEs.

Subjects who terminate the study early will have the same assessments as at follow-up (Day 30).

Subjects will be admitted on Day 119, before their Day 120 long-term follow-up visit.

8.4. Assessments

8.4.1. Sampling time points and additional tests

With the Sponsor's approval, additional time points may be introduced, and changes to time points may be made, if there is reason to believe that the change might improve the quality of the data (for example, if it is believed that an important effect of emodepside is occurring at a time when no measurements are scheduled), or if extra procedures are needed in the interest of subject safety. However, the total volume of blood taken in the trial will not exceed the value given in Section 8.4.4, unless in the opinion of the Investigator, it's in the subject's best interest that extra blood is taken for additional safety tests.

An additional 48 h' residence on the ward, and additional outpatient visits, will be permitted in the event of a technical failure, and/or if extra observations or samples of

blood are needed.

In the case of any samples for pharmacokinetic analysis, the following will not be regarded as protocol deviations:

- Deviations of not more than 5 min on measurements scheduled up to and including 4 h after a morning dose;
- Deviations of not more than 15 min on measurements scheduled from after 4 h to 24 h after a morning dose;
- Deviations of not more than 1 h on measurements scheduled more than 24 h after a morning dose; and
- Deviations of not more than 2 days on measurements scheduled for outpatient visits, the Follow-up visit, and long-term follow-up visits.

For all other procedures, the following will not be regarded as protocol deviations:

Table 7. Permitted deviation windows for all other procedures¹

Time point		Deviation window in relation to the scheduled time point
Day -1	Days 0-9	
Pre -24 h	Pre-dose (0 h)	Within 75 min before
-24 h to -23.5 h	Up to and including 30 min after the morning dose	± 5 min
After -23.5 h to -20 h	After 30 min to 4 h after the morning dose	± 10 min
After -20 to -12 h	After 4 h to 24 h after the morning dose	± 15 min
NA	more than 24 h after the morning dose	± 1 hour ²

1. Urine collection for laboratory safety tests will be within 2 h of the scheduled time point and all pre-dose urine samples will be collected pre-dose.
2. Deviations at outpatients visits (during Days 15 to 30) are ± 2 days, as shown in the in Schedule of events (Section 5)

8.4.2. PK assessments

Blood samples assaying the concentration of emodepside and its metabolites in plasma will be collected at the time points indicated in the Schedule of events (Section 5). The exact date and time of PK blood sampling will be recorded in the CRF.

Blood samples for PK purpose will be taken from either arm. Samples will be collected either by cannulation or by venepuncture. After processing, samples will be frozen and transported on dry ice to the Bioanalysis Laboratory. Detailed instructions for collection, processing, storage, and transport of samples will be provided in the Study Procedures Manual. Blood volumes for PK samples are shown in Section 8.4.4.

Plasma will be analysed for emodepside using a validated assay method. Full details of the method will be presented in a separate document and all the results will be reported in the bioanalytical report at the end of the study. On Profile Days (Day 0 and Day 9), frequent blood samples will be collected for PK estimation and emodepside plasma concentrations. On each treatment period, the following PK parameters of emodepside will be derived for each subject:

Single Dose Day 0 parameters

AUC ₁₂	The area under the concentration-time curve from time zero (pre-dose) to 12 h will be calculated using a trapezoidal method.
AUC ₂₄	The area under the concentration-time curve from time zero (pre-dose) to 24h will be calculated using a trapezoidal method.
AUC _{12/D}	The area under the concentration-time curve from time zero (pre-dose) to 12 h, corrected for dose
AUC _{24/D}	The area under the concentration-time curve from time zero (pre-dose) to 24h, corrected for dose
AUC _{12,norm}	The area under the concentration-time curve from time zero (pre-dose) to 12 h corrected by dose and body weight
AUC _{24,norm}	The area under the concentration-time curve from time zero (pre-dose) to 24h corrected by dose and body weight
C _{max}	The observed maximum plasma concentration measured in a subject after dosing identified by inspection of the drug concentration vs. time data.
C _{max/D}	The observed maximum plasma concentration measured in a subject after dosing identified by inspection of the drug concentration vs. time data, corrected for dose.
C _{max,norm}	The observed maximum plasma concentration corrected by dose and body weight
t _{max}	The time at which C _{max} was apparent, identified by inspection of the drug concentration vs. time data.
MRT _{last}	Mean Residence Time from time zero (pre-dose) to the time of last quantifiable concentration will be calculated using

$$MRT_t = \frac{AUMC_t}{AUC_t}$$

Where AUMC_t is the area under the first moment of the concentration-time curve from time zero (pre-dose) to the time of last quantifiable concentration

V_z/F Apparent volume of distribution will be calculated using the following formula:

$$V_z / F = \frac{Dose}{\lambda_z \bullet AUC_\infty}$$

Multiple Dose Day 9 parameters

λ_z	The terminal rate constant will be estimated by log-linear regression analysis on data points visually assessed to be on the terminal log-linear phase.
$t_{1/2}$	The terminal half-life will be calculated according to the following equation: $t_{1/2} = \ln 2 / \lambda_z$.
$t_{1/2,dom}$	The dominant half-life will be calculated from the terminal slope of the log concentration-time (0-24h) curve according to the following equation: $t_{1/2,dom} = \log_e 2 / \lambda_z$
AUC_{last}	The area under the concentration-time curve from time zero (pre-dose) to the time of last quantifiable concentration will be calculated using a trapezoidal method.
AUC_{last}/D	The area under the concentration-time curve from time zero (pre-dose) to the time of last quantifiable concentration, corrected for dose.
$AUC_{last,norm}$	The area under the concentration-time curve from time zero (pre-dose) to the time of last quantifiable concentration corrected by dose and body weight
AUC_{12}	Area under the plasma concentration-time curve during a 12 h dosing interval
AUC_{12}/D	Area under the plasma concentration-time curve during a 12 h dosing interval corrected for dose
$AUC_{12,norm}$	Area under the plasma concentration-time curve during a 12 h dosing interval corrected by dose and body weight
AUC_{24}	Area under the plasma concentration-time curve during a 24 h dosing interval
AUC_{24}/D	Area under the plasma concentration-time curve during a 24 h dosing interval corrected for dose
$AUC_{24,norm}$	Area under the plasma concentration-time curve during a 24 h dosing interval corrected by dose and body weight
AUC_{∞}	The area under the plasma drug concentration vs. time curve from time zero to infinity.
AUC_{∞}/D	The area under the plasma drug concentration vs. time curve from time zero to infinity, corrected for dose.
$AUC_{\infty,norm}$	The area under the concentration-time curve from time zero to infinity corrected by dose and body weight
$\%AUC_{extrap}$	Percentage of AUC_{∞} extrapolated from from t_{last} to infinity, using the following formula
	$\%AUC_{extrap} = \frac{100 \times AUC_{t-\infty}}{AUC_{\infty}}$
$C_{max,ss}$	The observed maximum plasma concentration measured in a subject at steady state, identified by inspection of the drug concentration vs. time data.
$C_{max,ss}/D$	The observed maximum plasma concentration measured in a

	subject at steady state, identified by inspection of the drug concentration vs. time data, corrected for dose.
$C_{\max,ss,norm}$	The observed maximum plasma concentration at steady state, corrected by dose and body weight
t_{\max}	The time at which C_{\max} was apparent, identified by inspection of the drug concentration vs. time data.
MRT_{∞}	The mean residence time extrapolated to infinity
CL_{ss}/F	Apparent total clearance from plasma at steady state will be calculated using the following formula:

$$CL_{ss} / F = \frac{Dose}{AUC_{\infty}}$$

V_z/F	Apparent volume of distribution will be calculated at steady state using the following formula:
---------	---

$$V_z / F = \frac{Dose}{\lambda_z \bullet AUC_{\infty}}$$

$RA(C_{\max})$	Accumulation ratio for C_{\max} , calculated from C_{\max} at steady state and C_{\max} after single dose
$RA(AUC_{\tau})$	Accumulation ratio for AUC_{τ} , calculated from AUC_{τ} at steady state and AUC_t after single dose, where $t = \tau$.

Steady state (days 1 – 9)

C_{trough}	Trough plasma concentration (measured concentration at the end of a dosing interval at steady state [taken directly before next administration]) obtained directly from the concentration-time data.
---------------------	--

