receiving placebo reported dry eye (n=1). All eye disorders AEs were of mild to moderate intensity, resolved spontaneously (without treatment), and were more frequently reported with highest dose (40 mg). Among them, the AEs of blurred vision, photophobia (“Increased ocular light sensitivity”), visual impairment (“distorted contrast perception”, “distorted colour perception”) reported by 8 out of 47 subjects receiving emodepside were considered as treatment-related by the Investigator. Also of note, at the highest dose (40 mg), lightheadedness (n=1), dizziness (n=1) or headache (n=1) were reported concomitantly to blurred vision.

None of the volunteers met any of the protocol-specified withdrawal criteria and overall tolerability to emodepside has been acceptable up to 20 mg. The presence of post-dose visual disturbances in subjects of Cohort 8 receiving either 40 mg solution or placebo may warrant some concern and escalation was stopped at this dose level.

The pharmacokinetic results obtained so far show that T_{max} for the LSF solution is consistently about 1 h post-dose when fasted. Mean C_{max} and AUC for the LSF solution have been roughly dose-proportional, with low to moderate inter-individual variability. The plasma half-life during the first 24 h is very short for a single dose of emodepside. After 3, 7, 16 and 47 h the maximum plasma concentration is reduced to 50%, 25%, 12.5% and 6.25% respectively. Terminal plasma half-life is 523 h. Although data of Cohort 9 (which was treated with a single dose of emodepside with food) are still under review, administration of the LSF of 10 mg with a high fat, high-calorie meal resulted in a clinically relevant food effect with a reduction of AUC to ~67%, C_{max} to 42% and a delay of the T_{max} up to 2.33 h. Therefore, the recommendation of administration of the emodepside (LSF) under fasted conditions is given.

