Detailed methodology for summary and statistical analyses of the data collected in this study will be documented in a Statistical Analysis Plan. This document may modify the plans outlined in the protocol; however, any major modifications of the primary endpoint definition and/or its analysis will also be reflected in a protocol amendment.

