31 AUG 2018
Date

[name]
Head of Translation, DNDi

Signature

[figure not shown]
29 August 2018
Date

[name]
Filarial Team Leader, DNDi

Signature

29 August 2018
Date

[name]
Head of Filarial Program, DNDi

Signature
[name]

29 August 2018
Date

3 Introduction

This Statistical Analysis Plan (SAP) is based on the current trial protocol (version 5, 25 July 2018). Where statistical methods differ substantially between this SAP and the protocol, that will be identified in this document.

This SAP describes the datasets and the statistical methods to be used for the reporting and analysis of all data collected during the trial.

The randomisation code will not be broken before this SAP is finalised. If a future protocol amendment necessitates a substantial change to the statistical analysis of the trial data, this SAP will be amended accordingly. If, after database lock, additional analyses are required to supplement the planned analyses described in this SAP, those unplanned analyses will not be described in an amended SAP, but they will be identified in the integrated clinical study report (CSR). Any deviations from this SAP will be documented in the CSR.

This SAP has been written in consideration of the following guidelines:

- International Conference on Harmonization (ICH) E9, Guidance for Industry: Statistical Principles for Clinical Trials (ICH E9 1998)¹; and
- ICH E3, Guidance for Industry: Structure and Content of Clinical Study Reports (ICH E3 1995)².

Pharmacokinetic analysis will be done using WinNonlin v7 on a Windows PC. Statistical analysis will be done using SAS[®] 9.3 on a Windows PC.

4 Study Objective(s) and Endpoint(s)

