1.2 AUC Calculations

The AUC will be calculated by a combination of linear and logarithmic methods. The linear trapezoidal method will be employed for all incremental trapezoids arising from increasing concentrations and the logarithmic trapezoidal method will be used for those arising from decreasing concentrations.

AUC_(0-∞) values with <20% of this area extrapolated will be reported.

It is acceptable to include data from profiles with >20% extrapolated as long as at least 80% of the profiles in the study have <20% of the AUC_(0-∞) as extrapolated area. In this instance, individual plasma concentration-time profiles for which the extrapolated areas are >20% of AUC_(0-∞) will be identified.

It is unacceptable to use AUC_(0-∞) data if >40% of the AUC has been extrapolated, except in specific situations which should be carefully justified in the study report.

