AUC _{24, norm} **	Area under the concentration-time curve from time zero to 24h corrected by dose and body weight	The AUC from time zero to 24h normalised by dose and body weight will be calculated as AUC ₂₄ /(Dose administered*body weight)	(h*ng/mL)/(mg*kg)	Y	-	AUCINTWD	AUC _{24, norm}

Text Symbol	Definition	Calculation	Typical Units	Log Transform	WNL	CDISC Controlled Terminology	TFL Symbol
AUC _∞	Area under the plasma concentration-time curve from time zero to infinity	The area under the concentration-time curve will be calculated using the (specified) trapezoidal method for the interval 0 to t _{last} (time t _{last} is the time at which the last non-zero level was recorded), plus the area under the exponential curve from t _{last} to infinity, calculated as follows: $AUC_{t-\infty} = \frac{\hat{C}_t}{\lambda_z}$ where \hat{C}_t is the predicted value of the concentration at t _{last} .	h*ng/mL	Y	AUCINF_pred	AUCIFP	AUC _{inf}
AUC _∞ /Dose	Dose-normalised AUC from time zero to infinity	The dose-normalised AUC from time zero to infinity will be calculated as AUC _∞ /Dose Administered	(h*ng/mL)/mg	Y	-	AUCIFPD	AUC _∞ /D
AUC _{∞,norm}	Area under the concentration-time curve from time zero to infinity corrected by dose and body weight	The AUC from time zero to infinity normalised by dose and body weight will be calculated as AUC _∞ /(Dose administered*body weight)	(h*ng/mL)/(mg*kg)	Y	-	AUCIFPWD	AUC _{∞,norm}
%AUC _{extrap}	Percentage of AUC _∞ extrapolated from from t _{last} to infinity	$\% AUC_{extrap} = \frac{100 \times AUC_{t-x}}{AUC_x}$	%	N	AUC_%EXTRAP_pred	AUCPEP	%AUC _{extrap}
Clearance, volume of distribution and mean residence time (after final dose)							
CL _{SS} /F	Apparent total clearance from plasma after oral administration	Apparent total clearance from plasma will be calculated using the following formula: $CL_{SS} / F = \frac{Dose}{AUC_t}$	L/h	Y	Clss_pred (actually derives Clss_F_pred for oral dose)	CLFTAU	CL _{SS} /F
V _z /F	Apparent volume of distribution after non-intravenous administration calculated at steady state	Apparent volume of distribution calculated at steady state will be calculated using the following formula: $V_z / F = \frac{Dose}{\lambda_z \cdot AUC_t}$	L	Y	Vz_pred (actually derives Vz_F_pred for oral dose)	VZFTAU	V _z /F

Text Symbol	Definition	Calculation	Typical Units	Log Transform	WNL	CDISC Controlled Terminology	TFL Symbol

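### Day 9 CLss/F and Vz/F are not apparent clearance and volume under either document's formula, and Day 9 AUC∞/D carries over drug from earlier doses

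*Protocol*

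**What the plan says.** Protocol Section 8.4.2, under the Day 9 multiple-dose parameters, states "Apparent total clearance from plasma at steady state will be calculated using the following formula" and gives CLss/F = Dose/AUC∞, with Vz/F = Dose/(λz × AUC∞). SAP Appendix B, Section 3.1.2 states "Apparent total clearance from plasma will be calculated using the following formula" and gives CLss/F = Dose/AUC_t, with Vz/F = Dose/(λz × AUC_t).

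Both documents also make Day 9 AUC∞/D a main secondary PK parameter (Protocol 2.2.3, SAP 4.2.2). The protocol defines it as "The area under the plasma drug concentration vs. time curve from time zero to infinity, corrected for dose". The SAP says "The dose-normalised AUC from time zero to infinity will be calculated as" AUC∞ over the dose administered. Neither removes the residue of earlier doses.

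Protocol Section 1.4 reports "Terminal plasma half-life is 523 h". Dosing lasts 10 days. Even so, Section 8.4.2 labels the Day 9 Cmax, CLss/F, Vz/F and accumulation ratios as steady-state quantities, and puts the Day 1–9 troughs under a steady-state heading.

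On precedence, Protocol Section 10 says of the SAP: "This document may modify the plans outlined in the protocol". SAP Section 3 undertakes: "Where statistical methods differ substantially between this SAP and the protocol, that will be identified in this document". The SAP text supplied does not identify this difference.

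**The concern.** Dose/AUC equals CL/F in two situations: AUC∞ after a single dose, or AUC over one dosing interval at steady state. Day 9 of this trial is neither.

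- **Protocol formula.** AUC∞ measured from the last dose includes everything still to be eliminated from the earlier doses, but only one dose is in the numerator. Clearance comes out too low. This would be so even at true steady state.
- **SAP formula.** AUCτ on Day 9 is still rising towards plateau because the slow phase has barely accumulated. Clearance comes out too high.

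Vz/F inherits the same errors, provided λz is right. A reader would take CLss/F, Vz/F, Cmax,ss and the accumulation ratios as plateau values, and AUC∞/D as exposure per unit dose. As defined, they are not. The two documents would also give very different numbers under one name.

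**Working it through.** The documents give no clearance figure to reproduce, so the check asks how far each formula departs from CL/F under linear superposition.

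**Inputs**
- Terminal half-life 523 h; concentration falls to 50, 25, 12.5 and 6.25% of Cmax after 3, 7, 16 and 47 h (Protocol 1.4).
- Once daily: n = 10 doses, τ = 24 h. Twice daily: n = 19 doses, τ = 12 h, taking the single Day 9 dose given in the Protocol Summary and Section 8.3.8. Sections 4.3 and 7.1 describe evening doses on Days 0–9; these passages must be reconciled.
- Last PK sample on Day 30: (30 − 9) × 24 = 504 h after the Day 9 dose.
- Assumption: slow-phase intercept 0.25–6% of Cmax. The decay points cap it at 6.25% × 2^(47/523) = 6.65%, but do not otherwise identify it: every value from 0 to 6% fits with RMS log error of 0.007 or less.

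**Accumulation of the slow phase.** 240/523 = 0.46 half-lives; 1 − 2^(−240/523) = 0.272.

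**Formulas.** Write the single-dose profile as C(t) = Σ Aᵢ exp(−kᵢt), with the slow half-life fixed at 523 h and absorption ignored (Tmax is about 1 h). Then:
- single-dose AUC∞ = Σ Aᵢ/kᵢ, and CL/F = Dose divided by this;
- Day 9 AUCτ = Σ (Aᵢ/kᵢ)(1 − exp(−n kᵢτ));
- Day 9 AUC∞ = Σ (Aᵢ/kᵢ)(1 − exp(−n kᵢτ))/(1 − exp(−kᵢτ));
- SAP overstatement = single-dose AUC∞ / Day 9 AUCτ;
- protocol understatement = Day 9 AUC∞ / single-dose AUC∞.

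**Worked case: once daily, intercept 1%.** The fit gives A = 0.835, 0.155, 0.010 with half-lives 2.37, 30.4 and 523 h. In units of Cmax × h:
- single-dose AUC∞ = 2.86 + 6.80 + 7.55 = 17.2;
- Day 9 AUCτ = 2.86 + 6.77 + 2.06 = 11.7, so the SAP fold is 17.2/11.7 = 1.47;
- Day 9 AUC∞ = 2.86 + 16.1 + 65.7 = 84.6, so the protocol fold is 84.6/17.2 = 4.92;
- extrapolated beyond 504 h: 65.7 × 2^(−504/523) = 33.7, and 33.7/84.6 = 39.8%.

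**Results**

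| Intercept | SAP too high, OD / BID | Protocol too low, OD / BID | Day 9 AUC∞ extrapolated, OD / BID |
|---|---|---|---|
| 0 (no slow phase) | 1.01 / 1.01 | 2.16 / 3.64 | – |
| 0.25% | 1.13 / 1.13 | 3.11 / 5.51 | 21.8% / 23.3% |
| 1% | 1.47 / 1.48 | 4.92 / 9.07 | 39.8% / 41.0% |
| 2% | 1.87 / 1.90 | 6.20 / 11.6 | 46.0% / 46.8% |
| 6% | 2.90 / 3.00 | 7.95 / 15.0 | 50.6% / 50.8% |

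Over 0.25–6%, Day 9 Cmax is 95% down to 52% (OD) and 93% down to 43% (BID) of its plateau value. The once-daily AUC accumulation ratio is 1.9–2.9 on Day 9, against 2.1–8.5 at plateau.

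**Cross-check.** A second profile (linear rise to 1 h, log-linear through the reported points, then a 523 h tail of 0.5–6.25% of Cmax at 47 h) gives SAP folds of 1.25–2.98 (OD) and 1.25–3.08 (BID). The protocol formula returns 0.12–0.26 (OD) and 0.07–0.15 (BID) of CL/F. The directions are the same at every intercept tried.

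**The case against.** The strongest reply is that the largest errors may never be reported. The SAP may supersede the protocol, so Dose/AUC∞ would normally give way to Dose/AUC_t. SAP Appendix B, Section 1.2 also restricts AUC∞: profiles above 20% extrapolation are admitted only if at least 80% of profiles are below 20%, and AUC∞ is not to be used "if >40% of the AUC has been extrapolated, except in specific situations which should be carefully justified in the study report". At intercepts of 0.25% or more the extrapolated share exceeds 20% throughout, so that rule would tend to withhold Day 9 AUC∞. What remains is a 1.1–3.0 fold error in two exploratory parameters. This limits the impact, but does not remove the point. The 0.25% floor is itself an assumption. Where the rule would let once-daily AUC∞ through (intercepts up to about 0.2%, where 18.9% is extrapolated), AUC∞/D is still 2.2–2.9 fold too high. The rule does not touch Dose/AUCτ.

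Second, the formulas were read from PDF by a program, and the SAP prints AUC_t, which its abbreviation list defines only as the area to time t. Tau is inferred from the codes CLFTAU and VZFTAU, and from the SAP's R_ac(AUC_t) standing where the protocol has RA(AUCτ). If t meant the last sample time, the SAP formula would understate clearance instead. It would still not be CL/F. The symbols should be checked against the PDF.

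Third, the tables are already headed Day 9, the half-life is stated openly, and daily troughs would show continuing accumulation. That is true, but the Day 1 trough, after one day of dosing, would still sit under a steady-state heading.

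**Conclusion.** The concern holds. As printed, the documents give different formulas for Day 9 CLss/F and Vz/F without flagging it, and neither yields apparent clearance or volume. Over an assumed slow-phase intercept of 0.25–6% of Cmax, the SAP formula is 1.1–3.0 fold too high. The protocol formula is 3.1–8.0 fold (OD) or 5.5–15 fold (BID) too low. The protocol error does not need the slow phase: without one it is still about 2.2 (OD) and 3.6 (BID) fold. The SAP error does need it, and is only about 6% at an intercept of 0.1%. The direction is secure if the reported 523 h phase exists and AUC_t means AUCτ; the size is a scenario range. The Vz/F folds also assume a correct λz.

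CLss/F and Vz/F are exploratory, and the primary safety objective and the predicted-Cmax stopping rule are unaffected. AUC∞/D, Cmax,ss and the accumulation ratios are secondary outputs, which makes the correction worth making before the analysis.

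**What to change.** - Use the same definitions in both documents, and record in the SAP any departure from the protocol.
- Do not report CLss/F or Vz/F from either formula as apparent clearance and volume.
- Do not divide Day 9 AUC∞ by the last dose alone.
- Label Day 9 Cmax, AUCτ and the Day 1–9 troughs by study day, and describe the accumulation ratios as Day 9/Day 0 ratios.
- If CL/F is wanted, prespecify a model fitted to all 45 planned plasma samples per subject with the full dosing history. SAP Appendix B, Section 1.3 gives only a weighting rule in case such a fit is used. State that the estimate extrapolates a terminal phase followed for 504 h, or 504/523 = 0.96 of one half-life, after the last dose.

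The first four items cost only wording and need no new data. The model is optional; it would have to be written into the SAP and would take perhaps a few days. The price is that no simple non-compartmental steady-state clearance is reported, and a fitted CL/F would itself lean on extrapolation.
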